9.18 Cardiovascular Monitoring

Patients will be closely monitored for signs of cardiac toxicity including assessments of CV AEs and symptoms.

If any of the following abnormalities are identified, an additional clinical investigation may be appropriate:

- Onset of new (i.e., not present at baseline or documented in the medical history) and clinically significant arrhythmia which is persistent (ie, confirmed on repeat assessment on a second visit), including but not limited to:
 - Sinus tachycardia (defined for the study as a HR \geq 100 beat/min and at least a 20 bpm increase from baseline)
 - Frequent ventricular premature contractions or atrial fibrillation
- Systolic hypertension (defined for the study as a SBP >160 mmHg and at least a 20 mmHg increase from baseline)
- Increase in troponin I vs. baseline and above the ULN.

Except in cases requiring immediate action for subject protection, the Investigator should consult with the Medical Monitor on how to best further determine rate/rhythm or blood pressure changes, in light of the known day to day variability in these physiological variables. The additional investigation may include the patient return to the study site within 72 hours for a confirmatory evaluation and repeat assessment. In this case, Sponsor and Medical Monitor should be notified within 48 h of the event. At the same time repeat lab samples are drawn, a PK sample may also be collected as deemed appropriate by Investigator and medical monitor.

Confirmatory evaluations may include:

- Obtaining a more detailed history of symptoms and prior or concomitant diseases;
- Obtaining a history of concomitant drug use (including non-prescription medications and herbal and dietary supplement preparations), alcohol use, recreational drug use, changes in activity, and special diets;
- Ruling out acute cardiovascular conditions, such as acute coronary syndrome, myocarditis, or acute aortic syndrome.
- Repeating ECG, troponin and CK-MB tests on at least one further occasion if abnormalities stabilize and the patient is asymptomatic;
- Considering requesting a cardiology consultation
- If immediate dose reduction or dose discontinuation is not required for concerns of subject safety, then at the Investigator's discretion more complete documentation may be obtained via, e.g. Holter monitoring or 24h Ambulatory Blood Pressure Monitoring before deciding to discontinue the subject.

If close monitoring is not possible, study drug should be discontinued temporarily, pending further evaluation by the Investigator in collaboration with the Medical Monitor and Sponsor. If a patient lives in a remote area, they can be tested locally and the results communicated to the investigator site promptly.

Study drug must be temporarily discontinued if the above abnormalities are confirmed. Frequency of subsequent repeat assessments will be determined by Sponsor and Medical Monitor.

Study drug may be resumed once abnormal results return to the normal range or to the patient's baseline values.

Study drug must be permanently discontinued if any of the following criteria are met:

1. A definite new cardiovascular diagnosis is confirmed that is considered to be probably related to study drug.
2. Abnormalities in symptoms, ECG, or laboratory biomarkers recur following re-introduction of study drug.
3. Abnormalities in symptoms, ECG, or laboratory biomarkers do not return to normal or baseline values.

The required Early Termination Visit assessments will be performed (see Section 6.6).

10 STATISTICS

10.1 Analysis Populations

The Intent-to-Treat (ITT) Population will include all patients who are randomized in the study and receive at least 1 dose of study drug. The ITT Population will be used for all efficacy analyses.

The Per Protocol Population will include all ITT patients who finish the Week 12 visit with valid MRI-PDFF measurements and do not have any major protocol deviations. Patients who are <80% compliant over the course of the initial 12-week Treatment Period will not be included in the Per Protocol Population.

The Safety Population will include all patients who are randomized in the study and receive at least 1 dose of study drug and will be used for all safety analyses.

Demographics, disposition, and study populations will be summarized descriptively.

10.2 Statistical Methods

10.2.1 Analysis of Efficacy

10.2.1.1 Primary efficacy analysis

The primary efficacy variable will be the percent change in MRI-PDFF from baseline to Week 12. Summary statistics (number of patients, mean, standard deviation, median, minimum, and maximum) at all visits and change from baseline will be provided. The primary efficacy analysis will be analyzed with an analysis of covariance (ANCOVA) model with treatment as a factor. For any patients in the ITT Population with a missing primary efficacy parameter, the control (placebo)-based pattern mixture model will be used. Based on PK obtained in healthy volunteers dosed for up to two weeks on doses of MGL-3196 from 20-200 mg per day, a significant fraction of patients randomized to an 80 mg dose may have their dose reduced to 60 mg after PK assessment at Week 2. The multiplicity (MGL-3196 60 mg versus placebo and MGL-3196 80 mg versus placebo) will be controlled by Dunnett's Test. The primary efficacy analysis will be performed based on the ITT Population and repeated based on the Per Protocol Population.

10.2.1.2 Secondary efficacy analysis

For the continuous secondary efficacy variables, the same ANCOVA model will be used. Normality will be tested for the model residuals. For certain efficacy variables (such as hsCRP and triglycerides), logarithm transformation may be performed prior to fitting the ANCOVA model. For the categorical secondary efficacy variables, Fisher's exact test will be used to compare the odds ratio between MGL-3196 doses versus placebo.

10.2.1.3 Other efficacy analysis

The same efficacy analyses used for the secondary efficacy variables will be used for the tertiary/exploratory efficacy variables.

10.2.1.4 Subgroup analysis

Subgroup analysis of the primary efficacy variable and/or selected secondary/other efficacy variables may be performed, such as gender (male/female), BMI ($\geq 30 \text{ kg/m}^2$ or $< 30 \text{ kg/m}^2$), and age group ($\geq \text{median}$ or $< \text{median}$).

10.2.2 Analysis of Safety

The safety endpoints for this study include: adverse events, safety laboratory assessments, vital signs, 12-lead ECGs, concomitant medications, and clinical assessments.

The adverse events will be coded using the latest version of the Medical Dictionary for Regulatory Activities (MedDRA). Treatment-emergent adverse events (TEAEs) will be defined as adverse events that are new or worsening after the first dose of study drug. A general summary of patients with TEAEs and SAEs will be tabulated with numbers and percentages of patients, and repeated for severity and relationship to study drug per treatment group. The number of adverse events leading to withdrawal and SAEs leading to death will also be summarized. The incidence of TEAEs will be summarized by body system and treatment group.

The safety laboratory data will be summarized by visit and by treatment group, along with changes from the baseline. The values that are <LLN or >ULN of the reference range will be flagged. Those values or changes in values that are identified as being clinically significant will be flagged. Laboratory abnormalities of special interest will be summarized.

10.2.3 Interim Analysis

Interim analysis is not designed for this study. However, an analysis will be performed once all patients reach Week 12 of the Treatment Period. The analysis will assess the efficacy of MGL-3196 on percent change in liver fat by MRI-PDFF.

10.2.4 Data Safety Monitoring Board

A Data Safety Monitoring Board (DSMB) will oversee the study to ensure patient safety and to advise if any dosing alterations are recommended. The DSMB will review safety including thyroid hormone effects, liver-related events (ie, clinically meaningful elevations in liver enzymes ALT, AST, and bilirubin), cardiovascular assessment (ie, changes in ECG, cardiac biomarkers, cardiac AEs, cardiac symptoms, arrhythmias, etc.), SAEs for trends in causality, and other efficacy (lipid parameters) and safety data as needed. The DSMB will perform regularly scheduled reviews the first scheduled for when 25 patients have received 6 weeks of treatment. Additional regularly timed meetings will be held and ad hoc meetings may also occur if determined by Madrigal and the DSMB.

10.2.5 Sample Size Determination

Approximately 117 patients in total will be randomized to 80 mg (2/3) or placebo (1/3) treatments. After PK assessment, a significant fraction of patients' combined AUC (MGL-3196 plus MGL-3196-M1) may exceed 5500 ng*hr/ml resulting in a dose reduction to 60 mg. In order to power the study appropriately for an efficacious dose (which may be ≥ 80 mg), randomization may continue until approximately 36 patients have continued at Week 4 on the 80 mg dose. It is estimated that the treatment difference of percent change in hepatic fat fraction from baseline to Week 12 between any dose of MGL-3196 and the placebo group is about -30%. With a common standard deviation for the percent change in hepatic fat fraction at 35%, 36 patients per group completing the Week 12 visit will provide 90% power with a 2-sample t-test. The significance level is set as 0.025 for the consideration of multiplicity in comparisons of 2 daily dosing regimens

of MGL-3196 versus the placebo group. The enrollment size is designed to allow for 10% drop out before the Week 12 visit, and as such, patients who drop out of the study will not be replaced.

With the sample size of 39 patients per treatment, the power for selected secondary efficacy endpoints was calculated. The baseline hepatic fat fraction is expected to be approximately 15% to 17%, thus the change from baseline to Week 12 in hepatic fat fraction is approximately -5.5% when comparing to placebo. With common standard deviation of change in hepatic fat fraction as 6%, 36 completed patients will provide 94% power for the study when evaluating the treatment effect in change of hepatic fat fraction.

In addition, the sample size is expected to provide meaningful liver biopsy-related data.

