3.1.2 Treatment Period

Following randomization, patients will begin the initial 12-week Treatment Period. Patients will undergo liver MRI-PDFF prior to the start of treatment (pre-dose), at the end of the initial 12-week Treatment Period (12 weeks after the start of treatment), and after continuing blinded treatment (MGL-3196 or placebo) for an additional 24 weeks (36 weeks after the start of treatment). A liver biopsy will be obtained prior to start of treatment (pre-dose) if the patient has not had a qualifying liver biopsy within 180 days of randomization and at 36 weeks. During the study, patients will return to the study site periodically for assessment of vital signs (temperature, pulse, respiratory rate, and seated blood pressure), 12-lead electrocardiogram (ECG), and clinical laboratory testing (hematology, chemistry, and urinalysis). During the study, patients who need to be placed on any excluded lipid lowering therapeutics will be discontinued from the study. Blood samples will be collected at specified times for the assessment of lipid parameters, thyroid hormone parameters, and other biomarkers. Patients will be evaluated for adverse events and concomitant medication use throughout the study. Patients should be monitored throughout the study for clinical signs and symptoms of hyper- or hypothyroidism.

A PK assessment will be made at Week 2 including a pre-dose fasting determination and assessments at 2, 4, 6, and 8 hours postdose. As described in PK section, patients who have a calculated $AUC_{inf} \leq 5500 \text{ ng*hr/ml}$ (combined MGL-3196 and MGL-3196-M1) will continue on 80 mg. For patients (~ 10%) with an $AUC_{inf} \leq 3000 \text{ ng*hr/ml}$ as described in Section 8 who are predicted to have exposure at 100 mg that remains $AUC \leq 5550$ based on a conservative calculation, the MGL-3196 dose will be increased from 80 mg to 100 mg at the Week 4 visit. For patients with combined $AUC > 5500 \text{ ng*hr/ml}$, the dose of MGL-3196 will be reduced to 60 mg per day on the Week 4 visit. Patients with $AUC_{inf} > 11,000$ (combined MGL-3196 and M1) plus $SHBG > 150\%$ increase from baseline at Week 2 (indicative that average or steady-state exposure is $> 11,000 \text{ ng*hr/ml}$) will be downtitrated to 40 mg at Week 4. If $SHBG \leq 150\%$, then patient will be downtitrated to 60 mg at Week 4, and patient's Week 4 SHBG and predose concentrations will be evaluated. If at Week 4 $SHBG > 150\%$ increase from baseline and predose

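### The stated 90% and 94% powers for two dose-versus-placebo comparisons are not secured: on the plan's own titration and drop-out figures about 63 active completers remain at 60 and 80 mg, against the 72 required

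*Protocol*

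**What the plan says.** Protocol 10.2.5, repeated in the Synopsis and SAP 4, sets out the sample size as follows.

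- Enrolment: "Approximately 117 patients in total will be randomized to 80 mg (2/3) or placebo (1/3) treatments".
- Effect on percent change in fat fraction: "between any dose of MGL-3196 and the placebo group is about -30" (percent). Spread: "With a common standard deviation for the percent change in hepatic fat fraction at 35" (percent).
- Power: "36 patients per group completing the Week 12 visit will provide 90% power with a 2-sample t-test". Alpha is 0.025 because two dosing regimens are each compared with placebo.
- Absolute change: a difference of 5.5 points with SD 6 gives 94% power at 36 completers.
- Drop-out: "The enrollment size is designed to allow for 10% drop out before the Week 12 visit".
- Group size: the power for secondary endpoints starts "With the sample size of 39 patients per treatment".
- Safeguard: "randomization may continue until approximately 36 patients have continued at Week 4 on the 80 mg dose".

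Protocol 10.2.1.1 names the two comparisons as 60 mg and 80 mg, each against placebo, with Dunnett's test for multiplicity. Protocol 3.1.2 describes the titration. A high Week 2 AUC moves a patient to 60 mg, or in some cases to 40 mg. The upward rule begins "For patients (~ 10%) with an" AUC at or below 3000 ng*hr/ml, and sends those patients to 100 mg at Week 4. SAP 3.7.2.1 analyses the primary variable as all active doses together against placebo.

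**The concern.** The calculation treats the trial as three groups of 39, but the randomisation creates only two groups, of about 78 and 39. How the 78 divide between 60 and 80 mg depends on exposure measured after randomisation. Nothing in the design fixes that division, and the protocol itself expects some patients to end up in neither dose group.

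The one safeguard is optional. It protects 80 mg and not 60 mg, and it counts patients still on 80 mg at Week 4, whereas the power statement counts Week 12 completers.

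At stake is whether a reader can take 90% and 94% as the power of each dose comparison. These figures are the only quantitative justification of size in either document.

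**Working it through.** **Inputs.** All are from Protocol 10.2.5 except the share moving to 100 mg (Protocol 3.1.2): 117 randomised 2:1, so 78 active and 39 placebo; difference 30 with SD 35; difference 5.5 with SD 6; alpha 0.025; 10% drop-out by Week 12; about 10% of active patients to 100 mg.

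**Method.** Two-sample t-test power from the noncentral t distribution with n1 + n2 − 2 degrees of freedom and noncentrality difference / (SD × √(1/n1 + 1/n2)). The Dunnett figures use the variance pooled over three groups and the two-sided 5% family-wise critical value for two comparisons with one control.

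**1. The plan's own figures reproduce.** At 36 v 36 and two-sided 0.025, power is 90.8% and 94.3%, and 36 is the smallest group size reaching 90%. The documents do not say whether the test is two-sided. One-sided 0.025 would give 94.8% and 97.0%, so two-sided is the reading that fits.

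**2. The drop-out allowance by itself.** 39 × 0.9 = 35.1 completers. A full allowance would need 36 / 0.9 = 40, and 39 covers 1 − 36/39 = 7.7%. At 35.1 v 35.1 power is 90.0% and 93.7% by t-test (90.9% and 94.3% by Dunnett), which agrees with the stated 90% and 94%.

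**3. Active patients available for the two dose comparisons.**
- Needed: 2 × 36 = 72 completers.
- After drop-out only: 78 × 0.9 = 70.2.
- After moves to 100 mg only: 78 × 0.9 = 70.2, already below 72 with nobody lost.
- After both: 78 × 0.9 × 0.9 = 63.2.
- Any moves to 40 mg reduce this further; the documents give no planned share.

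**4. Power for each dose with 63 active and 35 placebo completers.**

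| Split of the 63 | Dose group | t-test: percent / absolute change | Dunnett: percent / absolute change |
|---|---|---|---|
| Even | 31.6 (v 35.1 placebo) | 88.2% / 92.3% | 89.2% / 93.0% |
| 80 mg keeps 36 | 80 mg: 36 (v 35) | 90.4% / 93.9% | 91.2% / 94.5% |
| 80 mg keeps 36 | 60 mg: 63 − 36 = 27 (v 35) | 85.0% / 89.7% | 86.2% / 90.6% |

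The even split is the best case for the smaller of the two groups.

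**5. The extension rule.** If 36 patients are on 80 mg at Week 4 and up to 10% are then lost, 36 × 0.9 = 32.4 reach Week 12. Against 35.1 placebo completers that gives 88.7% and 92.6% by t-test. This is the lower end, because some of the 10% will have left before Week 4.

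**6. The SAP's pooled comparison.** At 70 active v 35 placebo completers and two-sided 0.05, power is 98.4% for percent change and 99.2% for absolute change.

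**The case against.** The strongest reply has four parts.

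- **Enrolment is not capped.** The total is approximate and randomisation may be extended. The summary tables under Amendment 6 show 84 active and 41 placebo patients treated, and 78 and 38 with Week 12 MRI, so 9 of 125 (7.2%) lacked it. This stands, and it rules out two stronger readings that a reader might infer. One is that 78 active patients cannot supply 36 completers at both doses. The other is that the gap between 39 and 40 per group means the stated powers are lost. The first treats an approximate number as fixed. The second is a one-patient rounding gap that leaves the powers at 90% and 94%. The reply does not settle the dose groups, however: the tables do not give evaluable numbers by dose, and the extension rule does nothing for 60 mg.
- **The planned test is Dunnett's, not two t-tests.** This also stands. It raises each per-dose figure by about one point, so any restated power must name its test.
- **The split is unknown and the classing of 100 mg patients is inferred.** The documents say only that a significant fraction may go to 60 mg, and Protocol 10.2.1.1 does not say where 100 mg patients belong. If they were counted with 80 mg, the shortfall would be 70 against 72, which is minor. For this reason only the even split and the case where 80 mg keeps 36 are shown. Splits with much smaller groups have no source in the documents.
- **The SAP pools the active doses.** This stands and confines the point to the Protocol's dose-specific comparisons. It does not rescue SAP 4, which still justifies the size by two dose regimens at 0.025 and so reports power for comparisons that SAP 3.7.2.1 does not perform.

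**Conclusion.** The point holds in a narrow form. The powers are calculated correctly for 36 completers per group, but the design does not secure 36 at both 60 and 80 mg. On the plan's own titration and drop-out figures about 63 completers remain for the two doses, against 72. At least one dose then has at best about 88% and 92% power by t-test (89% and 93% by Dunnett). The 60 mg comparison has about 85% and 90% (86% and 91% by Dunnett) if 80 mg keeps 36.

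This rests on a two-sided test, equal drop-out across groups, 100 mg patients belonging to neither dose group, nobody at 40 mg, and active enrolment near 78. The loss is a few points, and the pooled comparison in the SAP is amply powered. The documents therefore do not support calling the trial underpowered overall. The defect is a stated per-dose power that the design leaves to chance.

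**What to change.** In Protocol 10.2.5, the Synopsis and SAP 4, change wording only:

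1. Say that 39 per treatment is not fixed by the randomisation, because the 60/80 mg division follows from Week 2 pharmacokinetics.
2. Replace the stated powers with the expected completers and power per dose under the plan's own titration and drop-out figures. These are about 35 on placebo and about 63 at 60 and 80 mg together, with the even-split and 36/27 results above. Name the test used and say how 40 mg and 100 mg patients are classed.
3. Express the rule for continuing randomisation in Week 12 completers, or state the power that 36 patients on 80 mg at Week 4 would give.
4. In SAP 4, add the power of the comparison the SAP performs: pooled active v placebo, about 98% at 70 v 35 and two-sided 0.05.

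No patients are added and no dosing rule changes. The cost is that the per-dose powers read slightly less favourably.

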11 DATA MANAGEMENT AND RECORD KEEPING

11.1 Data Management

11.1.1 Data Handling

Data will be recorded at the site on eCRFs and reviewed by the clinical research associate (CRA) during monitoring visits. The CRAs will verify data recorded in the EDC system with source documents. All corrections or changes made to any study data must be appropriately tracked in an audit trail in the EDC system. An eCRF will be considered complete when all missing, incorrect, and/or inconsistent data has been accounted for.

11.1.2 Computer Systems

Data will be processed using a validated computer system conforming to regulatory requirements.

11.1.3 Data Entry

Data must be recorded using the EDC system as the study is in progress. All site personnel must log into the system using their secure user name and password in order to enter, review, or correct study data. These procedures must comply with Title 21 of the Code of Federal Regulations (21 CFR Part 11) and other appropriate international regulations. All passwords will be strictly confidential.

11.1.4 Medical Information Coding

For medical information, the following thesauri will be used:

- Latest version of MedDRA for adverse events and medical history, and
- World Health Organization Drug Dictionary for prior and concomitant medications.

11.1.5 Data Validation

Validation checks programmed within the EDC system, as well as supplemental validation performed via review of the downloaded data, will be applied to the data in order to ensure accurate, consistent, and reliable data. Data identified as erroneous, or data that are missing, will be referred to the investigative site for resolution through data queries.

The eCRFs must be reviewed and electronically signed by the Investigator.

11.2 Record Keeping

Records of patients, source documents, monitoring visit logs, eCRFs, inventory of study product, regulatory documents, and other Sponsor correspondence pertaining to the study must be kept in the appropriate study files at the site. Source data is defined as all information in original records and certified copies of original records of clinical findings, observations, or other activities in a clinical study necessary for the evaluation and reconstruction of the clinical study. Source data are contained in source documents (original records or certified copies). These records will be retained in a secure file for the period as set forth in the Clinical Study Agreement. Prior to transfer or destruction of these records, the Sponsor must be notified in writing and be given the opportunity to further store such records.

12 INVESTIGATOR REQUIREMENTS AND QUALITY CONTROL

12.1 Ethical Conduct of the Study

Good Clinical Practice is an international ethical and scientific quality standard for designing, conducting, recording, and reporting studies that involve human patients. Compliance with this standard provides public assurance that the rights, safety, and well being of study patients are protected, consistent with the principles that have their origin in the Declaration of Helsinki, and that the clinical study data are credible.

